6.3 Primary endpoint

Arm 1 -

Outpatient - CGM findings reflect patient's fingerprick glucose readings

- Episodes of true hypoglycaemia (as decided by finger prick glucose testing) are captured by the CGM device

- CGM detects hypoglycaemia whilst patient is asleep

Inpatient - 72 hour fast - CGM device calls hypoglycaemia when fingerprick/lab glucoses also do

Arm 2 -

Blinded phase - CGM findings reflect patient's fingerprick glucose readings - any episodes of true hypoglycaemia (as decided by fingerprick glucose testing) are captured by CGM device

unblinded phase - CGM recordings help with titration of anti hypoglycaemic medications and this reduces overall incidence of hypoglycaemic episodes or duration of time spent in hypoglycaemic range

For patients experiencing asymptomatic hypoglycaemic episodes, a reduction in asymptomatic hypoglycaemic episodes and regaining of hypoglycaemic symptoms.

For patients with symptomatic hypoglycaemia, a reduction in symptomatic episodes.

7. Study population

Clinicians in the endocrinology department at St Bartholomew's hospital will be notified of this study and encouraged to refer forward suitable patients from their clinics.

Arm 1

Patients referred to the endocrinology department at St Bartholomew's hospital for investigation of suspected hypoglycaemia by either GPs or other clinical teams in the same or external NHS trusts will be referred onwards to the study team by the doctor that sees them for their routine clinical care.

Arm 2

Patients known to the endocrinology department at St Bartholomew's hospital with hypoglycaemia that are medically managed or who are to start medical management will be referred to the study team by the doctor that sees them for their routine clinical care.

Some patients who are found to have hypoglycaemia through arm 1 of this study will be automatically offered the chance to partake in arm 2 if they are to have medical treatment.

No vulnerable groups will be included – all patient will be able to give valid consent on their own behalf
All patients will be able to understand sufficient English to give informed consent on their own behalf.

Inclusion Criteria

Able and willing to give informed consent. No vulnerable adults will be included.
Either conventional gender, or non-binary.
Age >18 years
Any ethnicity
Any socio economic group
Medical condition as detailed above – arm 1 under investigation for possible/probable hypoglycaemia

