Arm 2 – on medical therapy for established hypoglycaemia

Exclusion criteria

Unwilling or unable to give consent
Unable to speak sufficient English to give consent and understand study requirements
Age<18
Lack of capacity to consent
Underlying hepatic condition
Current excessive alcohol consumption (men regularly consuming >50 units/week, women >35 units/week)
Diabetes Mellitus
Current use of Diabetic medication or insulin
Currently pregnant
Any patient on haemo or peritoneal dialysis

Length of study participation

Arm 1 - investigation of hypoglycaemia - maximum of 10 days of monitoring (5 days as an outpatient, max 5 days as an inpatient).
Arm 2 - evaluating anti hypoglycaemic drugs - maximum of 10 days of initial monitoring (investigator and patient blinded to CGM results), then up to a maximum of a further 20 days (unblinded) monitoring, likely to be far less than this though.

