Patients who have been diagnosed with spontaneous hypoglycaemia which requires medical therapy will be given a CGM kit and a finger prick glucose monitoring device and glucose monitoring diary. Patients will take the standard medical therapy and perform finger prick glucose testing when they experience symptoms that they attribute to hypoglycaemia. These values will be recorded in the glucose monitoring diary. After (up to) 10 days of blinded CGM monitoring, the diary and CGM data will be reviewed. A member of the endocrine team (consultant or registrar with consultant approval) will then make changes to the medical therapy in order to abolish any remaining episodes of hypoglycaemia. Patients will then wear the CGM device in unblinded mode for up to a further 20 days (though likely to be far less) in order to facilitate further medication titrations. Patients will be asked to confirm low CGM glucose readings during this time with a finger prick glucose measurement.

The study organisers will observe the glucose data obtained from the CGM and match it with finger prick glucose readings (from glucose monitoring diaries) and lab glucose data to check for concordance.

CGM data (in conjunction with glucose monitoring diaries) will be scrutinised and compared against drug regimens to see which doses needed to be altered, or where additional medication is required.

Patients will complete a modified Clarke and Gold hypoglycaemia questionnaire at the start of arm 2. They will complete an adapted questionnaire prior to surgery for their hypoglycaemia (if indicated) or at 6 months after the start of arm 2 – whichever comes first.

9. Study procedures

Arm 1

Patients will be recruited either through attendance at endocrinology outpatients at St Bartholomew's hospital or through inpatient transfer to St Bartholomew's hospital – both with suspected diagnoses of hypoglycaemia.

If attending the outpatients department with suspected hypoglycaemia and thought to be suitable for the study, then the patient will meet a member of the study team after their outpatient appointment or they will be offered an appointment to discuss the study at a mutually convenient time. Informed consent will be obtained during this meeting.

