Finger prick Glucose monitoring diaries will be collected from patients.

Arm 2 – CGM Data from each Dexcom device will be downloaded at the end of the blinded phase and analysed. Subsequently, CGM data will be viewed remotely and downloaded.

Finger prick Glucose monitoring diaries will be collected from patients.

Hypoglycaemia questionnaires will be completed with patients

Follow-up procedures

Patients with confirmed hypoglycaemia will remain under standard endocrinology follow up irrespective of whether they choose to partake in arm 2 of the study.

Patients completing arm 2 will remain under standard endocrine follow up at St Bartholomew's hospital, unless they decide to transfer their care elsewhere.

Participant withdrawal

Participants may withdraw at any time. Any data that has been collected up to that point will be retained.

End of study definition

The end of the study (specifically - the end of collecting new CGM data) for each individual patient will be when,

- Arm 1 – The patient completes the inpatient CGM monitoring period and are found not to have hypoglycaemia, OR they complete the inpatient CGM monitoring period, are scheduled for anti hypoglycaemic treatment but do not wish to proceed to arm 2 investigations.
- Arm 2 – The patient completes the initial blinded monitoring phase and analysis shows that no further drug titration is required OR the patient goes into the subsequent unblinded monitoring phase and drug titration abolishes most/all of the hypoglycaemic episodes OR the 30 days of CGM monitoring elapses – whichever occurs first. Patients will be asked to complete a

hypoglycaemia questionnaire prior to surgery to cure hypoglycaemia, or at 6 months after the start of arm 2.

10. Assessment and management of risk

11. Safety Information

Adapted From Dexcom's website <https://www.dexcom.com/safety-information>

Our annotations are in bold, italics and underlined

Dexcom G6 Continuous Glucose Monitoring System

Indications for Use

The Dexcom G6 Continuous Glucose Monitoring System (Dexcom G6 System) is a real time, continuous glucose monitoring device indicated for the management of diabetes in persons age 2 years and older.

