12.2 Method of analysis

P<0.05 will be considered statistically significant

Arm 1

Positive and negative predictive value of CGM diagnosis of hypoglycaemia as an outpatient or an inpatient vs 72 hour fast (considered the 'gold standard')

Arm 2

In each patient, comparison of number of episodes of hypoglycaemia by finger prick glucose vs CGM vs symptoms during CGM blinded phase.

Severity of hypoglycaemia excursions

Amount of time spent in the hypoglycaemic range after medication titration – as measured by area under the curve on a time vs glucose graph generated by CGM machine. Comparisons of mean hypoglycaemic frequency and time within hypoglycaemic range within patients (blinded vs unblinded phase) using paired T test.

Change in hypoglycaemia questionnaire score before/after CGMs monitoring and medication titration

Regain of symptomatic hypoglycaemia in patients with asymptomatic hypoglycaemia, reduction of symptomatic hypoglycaemia in other patients.

13. Ethics

- Informed consent

Patients will be offered the chance to partake in the study should their treating consultant feel that they meet the inclusion criteria. Declining an invitation to take part in the study or leaving at any time means that the patient will default back to standard of care investigations. Their care will not be prejudiced or compromised in any way through either taking part or not taking part in the study.

- Recruitment

Only patients under investigation/treatment for hypoglycaemia at St Bartholomew's hospital will be considered for entry to the study. Patient being treated/investigated elsewhere who wish to be considered for the study would need to have their care transferred to St Bartholomew's by their GP/current endocrinologist.

- Inclusion / exclusion criteria

Inclusion/exclusion criteria is intended to screen out patients who have conditions that may affect their blood glucose (Diabetes Mellitus, underlying hepatic pathology) or in whom CGM is not recommended (pregnancy, critical illness) or in whom hypoglycaemia may be caused by extrinsic factors such as Diabetes medication.

- Study design

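### Arm 2 compares time in hypoglycaemia between two phases of unequal, variable length without scaling it to recorded time

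*Protocol*

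**What the plan says.** **The endpoint.** Protocol 6.3 says that, in the unblinded phase of arm 2, CGM should help titration and that this "reduces overall incidence of hypoglycaemic episodes or duration of time spent in hypoglycaemic range".

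**The analysis.** Section 12.2 lists "Amount of time spent in the hypoglycaemic range after medication titration", to be measured as an area under the glucose-time curve. It then plans "Comparisons of mean hypoglycaemic frequency and time within hypoglycaemic range within patients (blinded vs unblinded phase) using paired T test", with significance at P<0.05.

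**The phase lengths.** Section 8 (Arm 2) says: "After (up to) 10 days of blinded CGM monitoring, the diary and CGM data will be reviewed". Section 7 (Length of study participation) continues: "then up to a maximum of a further 20 days (unblinded) monitoring, likely to be far less than this though". Neither phase has a stated minimum.

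**What ends the unblinded phase.** Section 9 (End of study definition) closes CGM collection for a patient in this phase when "drug titration abolishes most/all of the hypoglycaemic episodes OR the 30 days of CGM monitoring elapses", whichever is first. Section 9 (Arm 2) moves patients into the unblinded phase if hypoglycaemia persists after the blinded review.

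**Scaling.** No section expresses time low per day, as a percentage of recorded time, or over matched windows. Section 11 discards the first 2 hours of CGM data but sets no denominator.

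**The concern.** A duration, an amount of time and an area all accumulate as recording goes on. If such a quantity is compared between a phase of up to 10 days and one that may last 20 days or only a few, the difference mixes any change in the patient's hypoglycaemia with the difference in wear time. This would be so even if every patient completed exactly 10 and 20 days, and it does not depend on the choice of the t test.

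At stake is the one between-phase test that 12.2 names for the unblinded-phase endpoint in 6.3. Depending on phase length, the same data could suggest that CGM-guided titration helped, did nothing or did harm.

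**Working it through.** The protocol gives no effect size, standard deviation, power or arm 2 number, so it has no figure of its own to reproduce. The check is on what the measure does when only the phase length changes.

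**Inputs.** Blinded length *b*: at most 10 days (sections 7 and 8). Unblinded length *u*: at most 20 days, expected to be far less (sections 7 and 8). The 3- and 5-day values below are illustrations.

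**Formula.** If a patient spends *r* minutes per day low in the blinded phase and *k·r* in the unblinded phase, the totals are *r·b* and *k·r·u*. Their ratio is *k·u/b*. With no change (*k* = 1) it is simply *u/b*.

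| Blinded (days) | Unblinded (days) | True rate ratio *k* | Ratio of totals | Appears as |
|---|---|---|---|---|
| 10 | 20 | 1 | 1 × 20/10 = 2.0 | 100% increase |
| 10 | 10 | 1 | 1 × 10/10 = 1.0 | no change |
| 10 | 5 | 1 | 1 × 5/10 = 0.5 | 50% reduction |
| 10 | 3 | 1 | 1 × 3/10 = 0.3 | 70% reduction |
| 10 | 20 | 0.5 | 0.5 × 20/10 = 1.0 | no change |
| 10 | 5 | 0.5 | 0.5 × 5/10 = 0.25 | 75% reduction |

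Dividing each total by its own recording time gives *k* in every row.

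**Which rows the end rule makes likely.** Apart from withdrawal, section 9 shortens the unblinded phase only when most or all episodes have been abolished. A patient who improves only partly, or not at all, runs towards the maximum (rows 1 and 5: a false increase or a masked benefit). A patient who responds well stops early (the direction of row 6: a real benefit exaggerated). Rows 3 and 4, a short phase with no change in rate, are arithmetically right but are not what the rule would usually produce.

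**Illustration at 20 against 10 days.** This is a paired t test, two-sided 0.05, 20,000 simulated studies. The assumptions, which are not in the protocol, are a gamma distribution with coefficient of variation 1 between patients and from day to day, the same lengths for everyone, and 10, 15 or 30 pairs.

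- True halving of the rate: a significant reduction appears in about 1%, 1% and 2% of studies on totals, against 76%, 95% and 99.9% on per-day values.
- No change in rate: a significant increase appears in 84%, 97% and 100% of studies on totals. Per-day rejections in both directions together are about 3 to 4%.

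**Illustration with an outcome-driven end.** This assumes no true change, 8 to 15 pairs, and a phase that stops once 2 or 3 consecutive days average below 20% of the blinded mean. The mean unblinded length was about 13 to 17 days. On totals, false increases occurred in 7 to 66% of studies and false reductions in well under 1%. The size depends on the assumed rule, but the direction agrees with the reasoning above.

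**The case against.** **The protocol never says total.** In 12.2, the word mean may govern both frequency and time, and frequency is ordinarily a rate, so an analyst could compute a mean daily time. The phrase about an amount of time also sits in its own sentence, which describes the period after titration and names no comparison between phases. This stands in part: the literal reading is not the only one. But 6.3 calls the same quantity a duration, 12.2 derives it from an area, and no sentence supplies a denominator.

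**A denominator is detail for a statistical analysis plan.** Often it is. Here, however, the protocol itself fixes the measure, its derivation, the contrast, the test and the threshold, and section 12 says no statistician is needed. The measure is specified in a form that does not suit the contrast, which is different from being left open.

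**A stronger reading that a reader might infer.** Since the unblinded phase is expected to be short, one might conclude that the test will usually show a false reduction when titration does nothing. The documents do not support this. Short phases for everyone with no effect conflict with the end rule in section 9, under which patients who do not improve tend to stay on the device longer. Nor is this the main test of the study: 6.3 lists several primary endpoints for both arms, and 12.1 calls the study a feasibility pilot.

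**Conclusion.** The point holds for the literal reading of 6.3 and 12.2: time low is unscaled and is compared between phases whose lengths differ by design and between patients. The length ratios (+100% at 20 against 10 days, -50% at 5 against 10, and a true halving hidden at 20 against 10) need only a constant daily rate within each phase. The simulated percentages also rest on assumed variances, arm 2 size and stopping behaviour, and serve only as illustration.

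The bias has no single direction. It works against the intervention in patients with long phases and for it in patients who respond and stop early. The text also permits a rate reading, so the right description is a measure that is badly fixed and should be corrected, not an analysis that is certain to mislead.

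**What to change.** In 6.3 and 12.2, define time low as percent of valid CGM time (or minutes per 24 hours of valid CGM) and episodes as a rate per 24 hours of valid CGM, separately for the blinded and unblinded phases. Exclude warm-up hours and signal gaps from the denominator. Run the paired comparison on these values. If the area under the curve is kept, scale it by the same recorded time.

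State beside this that scaling removes the length artefact only. Two sources of bias remain. The phase can end because episodes have stopped, so its length depends on the outcome. Patients enter the unblinded phase because hypoglycaemia persisted, so some fall is expected from regression to the mean. Both belong in the interpretation of a before-after comparison.

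Cost: one sentence in each section. The CGM data are already downloaded for both phases, so no new data are needed and no clinical procedure changes.

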13.1 Annual Safety Reporting

The CI will send an Annual Progress Report to the REC and the sponsor using the HRA template on the anniversary of the REC favourable opinion.

14. Public Involvement

No public involvement is planned

15. Data handling and record keeping

15.1 Data management

All electronic data will be stored on password protected NHS computers at an NHS site. Data back-ups will be made on NHS encrypted USB sticks, which will be stored alongside any paper based records (glucose diaries) in a locked cabinet within a locked room inside a hospital ward, accessed only by NHS staff.

CGM data will be obtained through downloading from the patient's CGM device onto a password protected NHS computer.

15.2 Source data

Glucose data will be obtained from;

- CGM devices during the study
- Fingerprick glucose devices and patient glucose diaries
- Lab measured venous glucose (and other blood tests) – from computerised hospital pathology system
- Formal diagnosis after inpatient investigation of diagnosis and supporting lab results – patient's electronic notes and pathology results from computerised record.

Medication record;

- Computerised patient record
- Paper drug chart

15.3 Confidentiality

Information related to participants will be kept confidential and managed in accordance with the Data Protection Act 2019, the General Data Protection Regulation (GDPR), NHS Caldecott Principles, the UK Policy Framework for Health and Social Care Research, and the conditions of NHS Research Ethics Committee favourable opinion.

Potential participants will be identified by their treating endocrine consultants (or deputy) in clinic or on the wards. The patient's permission to forward them to the study will then be sought. Once this permission is obtained then their details (hospital/NHSnumber) will be forwarded internally either by verbally or by secure NHS email.

Prior to publication, all data will be anonymised and is likely to be discussed as a whole rather than individually. In the event that an individual patient's results are discussed then they will be referred to in an anonymous way e.g. 'patient 1', with the numbering bearing no relation to their name, hospital/NHS number or date of birth.

All patients involved in the study will be under the care of the endocrine team at St Bartholomew's hospital. The study is being conducted by the same department and so as treating physicians, the study team already have legitimate access to patient

records. Patient records are held securely on (password and username protected) NHS computers and require a passcard and separate password to gain access.

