7.1 Inclusion criteria

Able and willing to give informed consent. No vulnerable adults will be included.
Either conventional gender, or non-binary.
Age >18 years
Any ethnicity
Any socio economic group
Medical condition as detailed above – arm 1 under investigation for possible/probable hypoglycaemia
Arm 2 – on medical therapy for established hypoglycaemia

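### Arm 1 recruitment leaves room for selective referral among patients booked for the 72-hour fast, so the planned PPV and NPV are at risk of selection bias of unknown direction and size

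*Protocol*

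**What the plan says.** Five places in the protocol bear on who enters arm 1.

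- Section 7, opening paragraph: clinicians in the department will be told of the study and "encouraged to refer forward suitable patients from their clinics".
- Section 7, Arm 1: patients sent to the department for investigation of suspected hypoglycaemia "will be referred onwards to the study team by the doctor that sees them for their routine clinical care".
- Section 9, Arm 1: an outpatient with suspected hypoglycaemia who is "thought to be suitable for the study" then meets the study team. For direct transfers, the same section has consent taken as early as convenient and mentions no suitability step.
- Section 13, Informed consent: "Patients will be offered the chance to partake in the study should their treating consultant feel that they meet the inclusion criteria".
- Section 15.3: "Potential participants will be identified by their treating endocrine consultants (or deputy) in clinic or on the wards".

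The arm 1 disease criterion in section 7.1 is "arm 1 under investigation for possible/probable hypoglycaemia". The arm 1 analysis in section 12.2 is "Positive and negative predictive value of CGM diagnosis of hypoglycaemia as an outpatient or an inpatient vs 72 hour fast". Section 5.4 explains that, in standard care, a patient is admitted for the fast only when clinical suspicion is strong enough. Section 12.1 describes a feasibility pilot of 30 patients, with no split between the arms.

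**The concern.** Arm 1 compares CGM with a reference test. Its predictive values describe patients sent for the fast only if enrolment within that group is unrelated to the likely result, or if the selection is at least visible. Clinicians who are encouraged, not required, to refer patients they think suitable can apply a second filter after the decision to fast. If that filter follows how convincing the history is, the enrolled share of fast-positive patients differs from the share among all those fasted, and PPV and NPV shift with it.

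The first primary objective is to see whether CGM can exclude hypoglycaemia and spare the patient a prolonged admission. NPV among patients who would otherwise be fasted is therefore the figure a reader will look for. No later analysis can recover patients who were never referred, so the question belongs in the recruitment text.

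**Working it through.** **Reading the passages together.** The arm 1 sentence in section 7 can be read as referral of every such patient. The opening of section 7 and the clinic step in section 9 can be read as referral of a chosen subset. Section 13 concerns eligibility, but the criterion being judged is possible or probable hypoglycaemia, so the judgement is partly one of suspicion. Section 15.3 gives the route of identification and no sampling rule. The text supports both readings and does not settle between them.

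**Plan's own figure.** There is none to reproduce. The protocol gives no sensitivity, specificity, prevalence or referral rate, and the sample size of 30 has no derivation. Everything below is illustration under stated assumptions.

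**Inputs (all assumed).** Se = Sp = 0.85. p is the fast-positive share among all patients fasted. r is the chance that a fast-positive patient is referred divided by the chance that a fast-negative patient is referred.

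**Formulas.**
- Enrolled fast-positive share: q = r·p / (r·p + 1 − p)
- PPV = Se·q / [Se·q + (1 − Sp)(1 − q)]
- NPV = Sp(1 − q) / [Sp(1 − q) + (1 − Se)q]

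**Worked case, p = 0.30.**
- r = 1 (no selection): PPV = 0.255 / (0.255 + 0.105) = 0.708; NPV = 0.595 / (0.595 + 0.045) = 0.930.
- r = 3: q = 0.9 / 1.6 = 0.5625. PPV = 0.4781 / (0.4781 + 0.0656) = 0.879; NPV = 0.3719 / (0.3719 + 0.0844) = 0.815.
- r = 0.5 (doubtful cases favoured): q = 0.15 / 0.85 = 0.176. PPV = 0.150 / (0.150 + 0.1235) = 0.548; NPV = 0.700 / (0.700 + 0.0265) = 0.964.

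| p | r | enrolled share q | PPV | NPV |
|---|---|---|---|---|
| 0.30 | 0.5 | 0.18 | 0.55 | 0.96 |
| 0.30 | 1 | 0.30 | 0.71 | 0.93 |
| 0.30 | 3 | 0.56 | 0.88 | 0.82 |
| 0.20 | 1 | 0.20 | 0.59 | 0.96 |
| 0.20 | 3 | 0.43 | 0.81 | 0.88 |

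**Different accuracy assumptions, p = 0.30.** With Se = 0.90 and Sp = 0.80, PPV/NPV are 0.66/0.95 at r = 1, 0.79/0.90 at r = 2, 0.85/0.86 at r = 3 and 0.49/0.97 at r = 0.5. The pattern is the same.

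**Sensitivity and specificity.** If referral depends only on the fast result, neither changes. They change only if severity is also selected. For example, if CGM detects 95% of florid and 60% of mild cases, a 50:50 mix gives 0.5 × 0.95 + 0.5 × 0.60 = 0.775, and a 75:25 mix gives 0.75 × 0.95 + 0.25 × 0.60 = 0.8625. That requires a further assumption.

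**Sampling error for scale.** The exact 95% interval is 0.60 to 0.98 for 13 of 15 correct, and 0.74 to 0.98 for 27 of 30.

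**The case against.** A reader might infer that arm 1 patients are picked on clinical suspicion and that the accuracy estimates are therefore biased, with sensitivity inflated. The documents do not support that. No passage says that clinicians choose among eligible patients by strength of suspicion. The arm 1 sentence in section 7 points towards referral of all, section 13 speaks of eligibility, and section 15.3 sits under confidentiality. The direction is also open. Clinicians might refer doubtful cases, where CGM could help most, and PPV would then fall and NPV rise. Even if likely cases were favoured, the lower NPV would understate the rule-out value of CGM. All of this stands.

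It is also true that suspicion selects patients for the fast before the study begins (section 5.4). Consecutive enrolment would not remove that selection and need not, because it defines the group who might be spared the fast. Referral to the study is a second filter inside that group, and that one is avoidable.

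In a pilot of 30 across two arms, sampling error alone is as wide as or wider than the shifts illustrated. That limits the weight of the point but does not answer it: a larger sample would reduce sampling error and leave selective referral in place.

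Finally, screening counts are often specified in an analysis plan or in trial records, and neither is at hand. Their absence from the protocol is not counted as a fault here.

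**Conclusion.** The point holds as a risk. The recruitment wording is loose and pulls two ways, suitability is undefined, and no rule requires that all eligible patients booked for the fast be approached. PPV and NPV, the arm 1 analysis, depend directly on who is enrolled. Under the assumed inputs with p = 0.30, a threefold referral ratio in favour of true cases costs 0.11 of NPV (0.93 to 0.82) and adds 0.17 to PPV (0.71 to 0.88). A ratio of 0.5 adds about 0.03 to NPV and takes about 0.16 from PPV. The true ratio, and even which side of 1 it lies on, cannot be learned from the protocol.

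Two stronger statements should not be made: that the estimates are biased, and that sensitivity and specificity are distorted. The first needs evidence of differential referral, and the second needs selection on severity as well. The matter limits interpretation of a pilot and is not a fatal flaw. It deserves correction because a better sampling method is available at one site for almost nothing, and analysis cannot repair the loss afterwards.

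**What to change.** 1. Reconcile the eligibility lists first. Section 7.2 omits the diabetes mellitus exclusion that appears in the synopsis and in the list within section 7. A rule to offer entry to all eligible patients needs one agreed list.
2. Reword sections 7, 9, 13 and 15.3 so that every consecutive patient booked or transferred for the 72-hour fast who meets those criteria is offered arm 1. Someone must still check eligibility, but there should be no separate suitability filter.
3. Keep a log of fasts performed, eligible, offered and consented, with reasons for each loss. Check it against the hospital's list of fasts at the monthly meeting already provided for in section 20.
4. Report those counts beside PPV and NPV, and limit the predictive-value statements to patients selected for the fast.

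The cost is protocol wording, a short log and a little administrative time. No extra patients, procedures or visits are needed. One hospital is involved, outpatients have a set admission date, and the study team belongs to the same department and already has access to the records.
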